#### 8.2.3.5 End of study

- Visit date
- Discontinuation or continuation (if interruption, date of last administration, reason for interruption)

- NIS physician's electronic signature for data integrity

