### 8.3.2 Endpoints

#### 8.3.2.1 Endpoints of safety

All reported adverse events in patients who take at least one dose of JARDIANCE DUO® will be noted.

[figure not shown]
Endpoints pertaining to safety will be presented as incidence rates of adverse events and will include:

[figure not shown]
- Adverse events
- Unexpected adverse events
- Serious adverse events
- Drug-related adverse events
- Non serious adverse drug reaction
- Adverse event of special interest
- Adverse events leading to discontinuation

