### 8.3.3 Assessment criteria

#### 8.3.3.1 Assessment of safety

[figure not shown]
- Adverse events (event name/ symptoms/ sign/ identify hypoglycemia symptoms)
- Onset date, End date
- Intensity (Mild/ Moderate/ Severe)
- Serious (Serious/ Non-Serious)
- Outcome of the event (Recovered/ Not yet recovered/ Sequela/ Fatal/ Unknown)
- Causality (Certain/ Probable/Likely/ Probable/ Possible/ Unlikely/ Conditional/ Unclassified/ Unassessable/ Unclassifiable)
- Factors other than JARDIANCE DUO® (None/ Concomitant medication/ Concomitant disease/ etc.)
- Action taken with study drug due to AE (Discontinued/ Reduced/ Increased/ Continue/ Discontinued and reintroduced/ Unknown/ Not applicable)
- Recurrence in reintroduced (Recurrence/ No-recurrence/ Unknown/ Not applicable)
- Adverse Event of Special interest (Not applicable/Vaginal moniliasis, vulvovaginitis, balanitis and other genital infection/Increased urination/Urinary tract infection/Volume depletion/ Diabetic Ketoacidosis, Decreased renal function, Hepatic injury defined by the alterations of liver parameters/Lower limb amputation)

- Investigator's comments(if needed)

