### Collection of AEs

The study design is of non-interventional nature and the study is conducted within the conditions of the approved marketing authorization. Sufficient data from controlled interventional studies are available to support the evidence on the safety and effectiveness of the studied JARDIANCE DUO®. For this reason the following AE collection and reporting requirements have been defined.

All adverse events occurred from the signing date on ICF to 30 days after last administration date of medication need to be collected, documented and reported to the sponsor using the AE reporting form of eCRF ([CRF13.1](#)).

All SAEs, ASAEs and AESIs must be reported within 24 hours of occurrence and via telephone/fax to the Local PV Manager (LPVM) of [REDACTED] using the NIS AE form ([13.2](#)). All non-serious Adverse Reactions associated with JARDIANCE DUO® (empagliflozin/metformin) and pregnancy monitoring forms must be reported within 7 calendar days of occurrence and via telephone/fax to the LPVM of [REDACTED]. If any new or further information to these events is available, a follow-up NIS AE report has to be sent to BI. All SAEs and non-serious AEs must include a causal relationship assessment from the physician.

All ADRs (serious and non-serious), including those persisting after study completion must be followed up until they are resolved, have been sufficiently characterized, or no further information can be obtained.

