2.2 Number of Subjects

The sample size of 600 patients is based on the requirement of the local regulatory authority (MFDS). As per regulation, long-term surveillance is necessary for the T2DM indication. Since T2DM is chronic disease it might be restrictive to collect safety and effectiveness data in short-term (12weeks) period, all patients will be enrolled for long-term (24weeks) surveillance.

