6.3 Demographics

- Continuous Data:

- Birth of year
- Body weight

- Categorical Data:

- Gender
- Birth of year
- Smoking status
- Early termination and reasons

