6.8.1 Summary of Adverse Events

The number of subjects with adverse events and their incidence (%) for each SOC and PT, 95% confidence interval for the incidence, and the number of cases will be included.

- Adverse events, Adverse drug reactions^a
- Serious adverse events, Serious adverse drug reactions
- Unexpected adverse events^b, Unexpected adverse drug reactions
- Unexpected serious adverse events, Unexpected serious adverse drug reactions
- Non serious adverse drug reaction^c
- Adverse event of special interest(AESI)^d
- Adverse events leading to discontinuation^e

^aAdverse Drug Reaction (ADR): any adverse drug reaction with causality (Certain/ Probable/Likely/ Possible/ Conditional- Unclassified/ Unassessable)

^bUnexpected adverse event: the event is not included in the latest approved local label

^cNon serious adverse drug reaction: any adverse reaction which does not meet the SAE criteria

^dAdverse event of special interest(AESI) is as following 8 events:

AESI (Adverse Event of Special interest)

- Vaginal moniliasis, vulvovaginitis, balanitis and other genital infection
- Increased urination
- Urinary tract infection (UTI)
- Volume depletion
- Diabetic Ketoacidosis (DKA)
- Decreased renal function:
 - Creatinine value shows a >2-fold increase from baseline and is above the ULN
- Hepatic injury defined by the following alterations of liver parameters:
 - An elevation of AST and/or ALT >3-fold ULN combined with an elevation of total bilirubin >2-fold ULN measured in the same blood draw sample.
 - An isolated elevation of AST and/or ALT >5-fold ULN (without an elevation of total bilirubin >2-fold ULN)
- Lower limb amputation
 - Amputation (i.e. resection of a limb through a bone)
 - Disarticulation (i.e. resection of a limb through a joint)
 - Auto-amputations (i.e. spontaneous separation of non-viable portion of the lower limb)

^eAdverse events leading to discontinuation: Reason of early termination is a 'due to Adverse event' and also action taken with study drug is 'Discontinued'

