7.2 Categorization

The categories for each item for categorical analysis are as follows. However, categories defined for categorical analysis of continuous data may be added or changed according to the distribution of the actually collected data.

Items	Category
• Children	< 19 years, ≥ 19 years
• Elderly	< 65 years, ≥ 65 years
• Pregnancy	Yes, No, Not Applicable
• Renal impairment	Yes, No
• Hepatic impairment	Yes, No
• Long-term follow-up	< 24 weeks,

Items	Category
	≥ 24 weeks
• Age	19 years ~ 29 years, 30 years ~ 39 years, 40 years ~ 49 years, 50 years ~ 59 years, ≥ 60 years
• Gender	Male, Female
• Smoking status	Never smoked, Ex-smoker, Currently smokes
• Family history of T2DM	Yes, No
• Disease period	< 1 year, 1 year ~ < 5 years, 5 years ~ < 10 years, ≥ 10 years
• Diabetes mellitus complications	Retinopathy, Neuropathy, Nephropathy, Vasculopathy, Etc.
• Medical history	Yes, No
• Allergy	Yes, No
• Renal failure	Yes, No
• Total administration period of JardianceDuo	< 12 weeks, 12 weeks ~ ≥ 24 weeks, ≥ 24 weeks
• Average of daily dose (Empagliflozin)	< 10 mg, 10 mg ~ ≥ 25 mg, ≥ 25 mg
• Average of daily dose (Metformin)	< 1,000 mg, 1,000 mg ~ ≥ 1,700 mg, 1,700 mg ~ ≥ 2,000 mg, ≥ 2,000 mg
• Other anti-diabetic agent	Yes, No
• Concomitant medications	Yes, No
• Discontinuation of study medication	Yes, No
• Severity	Mild, Moderate, Severe
• Serious AE	Yes, No
• SAE Category	Results in death, Immediately life-threatening, Persistent or significant disability/ incapacity, Requires patient hospitalization, Prolongs patient hospitalization, Congenital anomaly/ birth defect, Other comparable medical criteria
• Action taken	Continue, Reduced, Discontinued, Increased, discontinued and reintroduced, Unknown, Not applicable
• Recurrence according to reintroduced	Recurrence, No-recurrence, Unknown,

Items	Category
	Not applicable
• Causality	Certain, Probable/Likely, Possible, Unlikely, Conditional / Unclassified, Unassessable / Unclassifiable
• Factors other than JARDIANCE DUO	None, Concomitant medication, Concomitant diagnoses, Other
• Outcome	Recovered, Not yet recovered, Sequelae, Fatal, Unknown
• Therapy for the event	Yes, No
• Effectiveness	Effectiveness, Ineffectiveness

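### The SAP's two-field rule for AEs leading to discontinuation can fall below the count given by the event's own action code, and undercounts if the fields disagree

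*SAP*

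**What the plan says.** Protocol 8.3.2.1 names "Adverse events leading to discontinuation" as one of seven safety endpoints and does not define it. Monitoring safety is the primary objective.

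The definition comes from footnote e of SAP 6.8.1: "Reason of early termination is a 'due to Adverse event' and also action taken with study drug is 'Discontinued". It joins two different kinds of record.

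- **Event level.** Protocol 8.3.3.1 records, for each AE, "Action taken with study drug due to AE (Discontinued/ Reduced/ Increased/ Continue/ Discontinued and reintroduced/ Unknown/ Not applicable". SAP 7.2 carries the same seven codes: "Continue, Reduced, Discontinued, Increased, discontinued and reintroduced, Unknown, Not applicable". A permanent stop and a stop followed by restart have separate codes.
- **Subject level.** SAP 6.3 summarises "Early termination and reasons" among the demographic items. The nearest protocol source is the end-of-study record in 8.2.3.5: "Discontinuation or continuation (if interruption, date of last administration, reason for interruption".

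Neither document says what happens when the two records disagree, and the SAP plans no count of this endpoint on one field alone.

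**The concern.** The action item already states what was done with the drug because of that particular event, which is the question the endpoint asks. The termination reason cannot say which of a subject's AEs stopped the drug. Adding it as a further condition identifies no new events; it can only remove some.

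The protocol makes disagreement foreseeable. Section 8.9.1 plans to obtain AE information by telephone, letter or email from patients lost to follow-up. Section 8.3.1.3 excludes lost patients only when their safety information cannot be obtained. A patient reached in this way can remain in the safety set with an AE coded 'Discontinued' and a termination reason of loss to follow-up. That patient counts in the denominator but not in the numerator. Events are also collected after dosing stops: "All adverse events occurred from the signing date on ICF to 30 days after last administration date of medication".

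At stake is the incidence and confidence interval of a named safety endpoint, which would be biased downward to an extent the report would not show.

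**Working it through.** **No plan figure to reproduce.** The documents give no expected rate for this endpoint and no precision calculation: "The sample size of 600 patients is based on the requirement of the local regulatory authority (MFDS".

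**Step 1: logic.** Let A be the subjects whose termination reason is an AE, and B the subjects with at least one AE whose action is 'Discontinued'. Footnote e counts A∩B, and |A∩B| ≤ min(|A|, |B|). The count equals |B| only if every subject in B is also in A.

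**Step 2: records that fail one condition.**

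| Termination reason | Action for the AE | Footnote e | Action code alone |
|---|---|---|---|
| AE | Discontinued | counted | counted |
| Loss to follow-up or other | Discontinued | not counted | counted |
| None recorded | Discontinued | not counted | counted |
| AE | Unknown or Not applicable | not counted | not counted unless a query resolves the code |

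The last row is plausible for a fatal event. Changing the definition alone does not recover it, which is why the fix includes a query.

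**Step 3: illustration of size.** Inputs: n = 600 (planned enrolment; the actual denominator is the safety set, which may be smaller) and exact two-sided 95% intervals (SAP 5.5). Two inputs are assumptions because the documents do not give them: |B| = 12, 30 or 60 (2%, 5%, 10%), and a share d of B with another termination reason or none.

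Reported count x = |B| × (1 − d), rounded. For example, 30 × (1 − 0.20) = 24, and 24/600 = 4.00%. Exact limits: lower = Beta⁻¹(0.025; x, n − x + 1), upper = Beta⁻¹(0.975; x + 1, n − x).

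| d | B = 12 | B = 30 | B = 60 |
|---|---|---|---|
| 0% | 12: 2.00% (1.04–3.47) | 30: 5.00% (3.40–7.06) | 60: 10.00% (7.72–12.68) |
| 10% | 11: 1.83% (0.92–3.26) | 27: 4.50% (2.99–6.48) | 54: 9.00% (6.83–11.58) |
| 20% | 10: 1.67% (0.80–3.04) | 24: 4.00% (2.58–5.89) | 48: 8.00% (5.96–10.47) |
| 30% | 8: 1.33% (0.58–2.61) | 21: 3.50% (2.18–5.30) | 42: 7.00% (5.09–9.34) |
| 50% | 6: 1.00% (0.37–2.16) | 15: 2.50% (1.41–4.09) | 30: 5.00% (3.40–7.06) |

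**Step 4: comparison with the truth.** Miscoding can also push the count up. With 12 true cases all captured, and 0.5% of the other 588 subjects wrong on both fields together, the rule counts 12 + 588 × 0.005 = 14.94. It still does not exceed the action-code count.

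**The case against.** The case for leaving the rule alone has several good points.

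- **The protocol leaves the endpoint undefined.** The SAP fills a gap and contradicts nothing. Requiring two fields to agree is a legitimate choice in favour of specificity for a descriptive endpoint. This stands, but a permanent stop already has its own code. The subject-level field is therefore not needed to screen out temporary stops that are coded as such, and the SAP does not say how conflicts are settled.
- **Case counts by action taken are already planned.** SAP 6.8.2 gives them by SOC and PT, so events that fail footnote e would still appear there, as would those coded 'Discontinued and reintroduced'. This stands, and a separate line for restarts is unnecessary. What 6.8.2 lacks is the number of subjects, the incidence and the interval, and two tables in one report could differ without explanation.
- **Entry checks may force agreement.** Protocol 8.8 describes consistency checks at data entry. The eCRF is kept outside the protocol, so whether these two fields are cross-checked cannot be seen.

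A reader might go further and infer that the endpoint can only be undercounted. That does not follow: nothing is lost if the fields agree, and step 4 shows that an overcount against the truth is possible. A reader might also infer that a patient who stops the drug for an AE but still attends week 24 is always dropped. That assumes 'early termination' means leaving the study. Protocol 8.2.3.5 asks about interruption together with the last administration date, and 8.7.1 places the interruption reason with the medication information. Both suggest stopping the drug, in which case this patient would be counted. The documents do not settle the meaning. Nor do they show that the report will make tolerability look better than the data, since disagreement is possible but not demonstrated.

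**Conclusion.** The point holds as a weakness of definition. Footnote e yields a count equal to or lower than either single-field count, and it undercounts whenever a genuine AE discontinuation fails one of the two conditions. The size cannot be determined. It is zero under full agreement; with 30 of 600 subjects coded as discontinued, it would be 3 subjects at 10% disagreement and 15 at 50%. Those rates are assumptions.

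The conclusion that the count is bounded by the action code rests only on the wording of footnote e. That disagreement may occur rests on the plan to trace lost patients and on the absence of a reconciliation rule; it would be removed by an eCRF check forcing the fields to match. Sample size, power and significance level are unaffected. The rule should be changed because it can bias a named safety endpoint downward and the remedy is nearly free.

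**What to change.** Rewrite footnote e so that an AE leads to discontinuation when its own action taken with study drug is coded 'Discontinued', whatever the subject's termination reason. Report subjects, incidence, exact 95% interval and number of events on that basis.

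Before database lock, query and list discordant records in both directions:

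- AEs coded 'Discontinued' in a subject with another termination reason or none;
- subjects terminated for an AE with no AE coded 'Discontinued', including those whose action is 'Unknown' or 'Not applicable'.

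Leave 'Discontinued and reintroduced' in the existing action-taken table. In the same revision, state whether early termination refers to the drug or the study.

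The cost is one redefined footnote, one clarifying sentence, a discordance listing and a small amount of query work. The reported incidence may rise slightly.

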6.8.2 Adverse Events by Preferred Term

For the safety analysis set, the adverse event incidence status for the following items will be presented in detail. Using the latest version of MedDRA, the number of subjects with adverse events and their incidence (%) for each SOC and PT, 95% confidence interval for the incidence, and the number of cases will be included. At this time, even if two or more adverse events were expressed in one subject, if they fall under one category, they will be analyzed as one person within the category. In addition, one subject may be presented in duplicate in different adverse event categories.

- Adverse events, Adverse drug reactions
- Serious adverse events, Serious adverse drug reactions
- Unexpected adverse events, Unexpected adverse drug reactions
- Unexpected serious adverse events, Unexpected serious adverse drug reactions
- Non serious adverse drug reaction
- Adverse event of special interest(AESI)
- Adverse events leading to discontinuation

For the short-term use (< 24 weeks) and long-term use (\geq 24 weeks) subjects in the safety analysis set, the adverse event incidence status for the following items will be presented in detail. Using the latest version of MedDRA, the number of subjects with adverse events and their incidence (%) for each SOC and PT, 95% confidence interval for the incidence, and the number of cases will be included. At this time, even if two or more adverse events were

expressed in one subject, if they fall under one category, they will be analyzed as one person within the category. In addition, one subject may be presented in duplicate in different adverse event categories.

[figure not shown]
- Adverse events, Adverse drug reactions
- Serious adverse events, Serious adverse drug reactions
- Unexpected adverse events, Unexpected adverse drug reactions
- Unexpected serious adverse events, Unexpected serious adverse drug reactions

For all adverse events that have occurred, the number of cases by the following adverse event investigation items is presented. Additionally, the incidence status of adverse events by investigation item is presented in detail. Using the latest version of MedDRA, the number of cases of adverse events by SOC and PT will be included. At this time, even if two or more adverse events were expressed in one subject, if they fall under one category, they will be analyzed as one person within the category. In addition, one subject may be presented in duplicate in different adverse event categories.

- Severity of Adverse events
- Action taken with study drug due to Adverse events
- Recurrence according to reintroduced
- Causality
- Factor other than study drug
- Outcome of the event
- Therapy for the event

For the following categories, a list of events will be included:

- Serious adverse events
- Unexpected adverse events
- Unexpected serious adverse events
- Adverse events with Renal impairment
- Adverse events with Hepatic impairment

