## 8.7 DATA ANALYSIS

### 8.7.1 Analysis of demographic data

Demographic data and the health status of subjects for the safety evaluation will be analysed descriptively. For continuous data, mean, standard deviation, minimum value, and maximum value will be described, while for categorical data, frequency will be shown.

Parameters corresponding to demographic data are as mentioned below.

- ① Basic information and disease information
  - Age, gender, pregnancy, body weight, smoking status, diabetes mellitus complications, other medical history, disease period, Family history of T2DM, elderly (Age  $\geq$  65 years), renal impairment and hepatic impairment, allergy, long term use (over 24 weeks)
- ② Medication information
  - Concomitant medication, study drug administration status (total period of drug use, average of daily dose), reason for early interruption, any anti-diabetic agents

To assess the extent of preferential prescribing and the potential for channeling bias, data from the TRAJENTA DUO® (linagliptin/metformin) rPMS will be used as a comparator. The baseline characteristics of patients starting JARDIANCE DUO® for the first time will be compared to the baseline characteristics of patients who started TRAJENTA DUO® for the first time. Proportions and means (SD) of the baseline characteristics will be compared using absolute standardized differences (ASD), where an ASD of at least 10% will be considered a meaningful difference. p-values will also be calculated.

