### 8.7.2 Safety analysis

- ① Among the subjects of safety evaluation, the number of subjects with adverse event incurred and the number of adverse events incurred should be calculated, and the incidence rate of adverse events and the 95% confidence interval should be presented.
- ② The number and percentage of adverse events by type and category should be presented.

- ③ Analysis should be made using Chi-square test or Fisher's Exact test on the adverse event onset status by demographic data of subjects of safety evaluation.
- ④ To estimate any factors that are thought to influence the analyzed incidence rate of adverse events, logistic regression analysis should be conducted, and for statistically significant parameters, the meaning should be described.

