## **8.9 LIMITATIONS OF THE RESEARCH METHODS**

### **8.9.1 Loss to follow-up**

All efforts will be made to minimize loss to follow up, particularly in the tracking of lost patients. To the extent possible, occurrence of adverse event, at minimum, for patients lost to follow up will be obtained via patient visit/telephone/letter/email etc. This allows assessing the impact of informative censoring due to treatment discontinuation. Also, patients lost to follow up will be characterized compared to the remaining patients and reason and time point of loss to follow up will be evaluated.

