### **Expedited Reporting of AEs and Drug Exposure During Pregnancy**

The following must be reported by the investigator on the NIS AE form from signing the informed consent onwards until the end of the study:

Type of Report	Timeline
All Serious Adverse Events (SAEs), Always Serious Adverse Events (ASAEs) and Adverse	immediately within 24 hours

Event of Special interest	
* 13.2 SAE/ Non-Serious Adverse Reaction Report	
All AEs with fatal outcome * 13.2 SAE/ Non-Serious Adverse Reaction Report	immediately within 24 hours
All non-serious Adverse Reactions associated with JARDIANCE DUO® (empagliflozin/metformin) * 13.2 SAE/ Non-Serious Adverse Reaction Report	7 calendar days
All pregnancy monitoring forms * 13.3 Pregnancy Monitoring Form A, B	7 calendar days

The same timelines apply if follow-up information becomes available for the respective events. In specific occasions the Investigator could inform the Sponsor upfront via telephone. This does not replace the requirement to complete and fax the NIS AE form.

All other Adverse Events must be reported using eCRF within 2 weeks to the Sponsor.

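### The short- versus long-term use tables group patients by how long they stayed on drug, which adverse events can shorten, so the long-term column is not a 24-week risk

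*SAP*

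**What the plan says.** SAP 2.2 states that "all patients will be enrolled for long-term (24weeks) surveillance"; there is no planned 12-week cohort. SAP 6.8.2 first tabulates AEs for the whole safety set, then repeats the main categories "For the short-term use (< 24 weeks) and long-term use" (24 weeks or more) subjects. Each group gets its own number of subjects, incidence, 95% confidence interval and number of cases. No between-group test is named in 6.8.2, and no counting window is stated there.

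SAP 7.1 derives the total administration period from dosing dates, closing an open last interval at the last visit. Protocol 10.2 sets AE collection as "All adverse events occurred from the signing date on ICF to 30 days after last administration date of medication". Protocol 8.9.1 says of obtaining AE information on lost patients: "This allows assessing the impact of informative censoring due to treatment discontinuation".

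Protocol 8.7.1 includes among the demographic data "long term use (over 24 weeks") and, under medication information, "study drug administration status (total period of drug use, average of daily dose), reason for early interruption". Protocol 8.7.2 then says: "Analysis should be made using Chi-square test or Fisher's Exact test on the adverse event onset status by demographic data". SAP 5.5 makes multiple logistic regression depend on more than two variables being significant in that kind of analysis.

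SAP 4 names a long-term safety analysis set in section 4.3, and SAP 6.8 names a section 6.8.3. Neither section is in the text available.

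**The concern.** When every patient has the same planned follow-up, only what happens after the first dose can separate short from long use. AEs are one of the things that happen. Patients whose AE led to permanent stopping before week 24 are removed from the long-term column by construction, while AE patients who carried on remain in it. Patients who stop for other reasons go to the short-term column with less observation time. These two forces act in opposite directions on the contrast, and neither is an effect of duration.

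Safety is the primary objective, and among the AE tables in the available SAP text this is the one labelled long-term use. A reader could take its second column for the risk over 24 weeks of treatment, or the contrast for the effect of longer exposure. The available SAP text has no AE analysis by time since first dose that would answer either question.

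The testing plan has a related problem. Everyone who stopped because of an AE had an AE, so that reason is circular as a factor for AE occurrence. Duration of use is not circular, but it is partly a result of AEs. Protocol 8.7.2 asks for the meaning of significant parameters in the logistic regression to be described.

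**Working it through.** **Inputs.** From the documents: 600 patients (SAP 2.2), 24 weeks = 168 days, collection to 30 days after last dose (protocol 10.2), exact 95% intervals (SAP 5.5). The documents give no AE or stopping rates, so there is no planned figure to reproduce. Assumed: 24-week AE risk p = 20% at constant hazard (no duration effect), a fraction q of AEs causing permanent stopping, 8% stopping for other reasons spread evenly over 24 weeks, and Visit 3 on day 168.

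**Long-term column, counted to Visit 3.** Among patients still on drug at week 24, incidence = p(1−q)/(1−pq).
- q = 10%: 0.18/0.98 = 18.4%
- q = 25%: 0.15/0.95 = 15.8%
- q = 40%: 0.12/0.92 = 13.0%

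Simulation with millions of patients per setting gives 18.4, 15.8 and 13.1%. The last differs slightly because the +1 day in SAP 7.1 lets a stop on day 167 count as 168 days.

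**Counted to 30 days after last dose.** With r = 1 − 0.8^(30/168) = 3.9%, incidence = [p(1−q) + (1−p)r]/(1−pq). This is below p only when q > r/p = 0.0391/0.20 = 19.5% (18.6% at p = 10%, 20.6% at p = 30%).

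| AEs causing stopping | To Visit 3: short / long / full set | To last dose + 30 days: long / full set |
|---|---|---|
| 0% | 13.4 / 20.0 / 19.5% | – |
| 10% | – / 18.4 / 19.5% | 21.6 / 22.4% |
| 25% | 45.1 / 15.8 / 19.5% | 19.1 / 22.4% |
| 40% | – / 13.1 / 19.5% | 16.5 / 22.4% |

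The contrast reverses from 13.4 versus 20.0% to 45.1 versus 15.8% although the AE hazard never changes.

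**Against sampling error.** At q = 10% about 541 patients are long-term; the exact interval is 15.1–21.8%, which contains 19.5%. At q = 25% about 525 are long-term; the half-width is roughly 1.96 × √(0.158 × 0.842/525) = 3.1 points, against a gap of 19.5 − 15.8 = 3.7.

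**When the long-term figure falls below the full set over the same window.** The crossover in q depends on other stopping:
- 8%, evenly spread: about 3–7%, across counting windows and plausible Visit 3 timing
- 20%, evenly spread: about 8–12%
- 20%, all in weeks 0–8: about 15–20%

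Below the crossover, early stoppers with short observation dilute the full set more than AE stopping depletes the long-term group.

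**Circular factor.** Take 120 AE patients in 600 and compare those who stopped for an AE with everyone else. Two such patients give Fisher p = (120 × 119)/(600 × 599) = 0.040; three give 0.040 × 118/598 = 0.008.

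The yes/no discontinuation item in SAP 7.2 behaves differently. With 48 other-reason stoppers (8% of 600), of whom 13.4% had an AE, adding two or three AE stoppers gives p = 0.58 or 0.85.

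**The case against.** Much can be said for the plan. Section 6.8.2 is descriptive, reports the whole safety set first and tests nothing between the two groups. AEs leading to discontinuation are tabulated in the full set, so the depletion is partly visible. Protocol 8.7.2.1 also plans to describe lost patients with the reason and time of loss. The sample size is a regulatory number, and elaborate survival methods are not obligatory in descriptive surveillance. All of this stands and limits the weight of the point. None of it makes the long-term column a 24-week risk.

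Four stronger readings are tempting and are not supported:
- **The long-term figure is always below the full set.** It is not; with frequent early stopping for other reasons and few AE-driven stops it is higher.
- **It always understates the 24-week risk.** Under the protocol 10.2 window it does so only when about 20% or more of AEs cause stopping.
- **The protocol gives two rival windows for tabulation.** The text "from signing the informed consent onwards until the end of the study" governs what goes on the expedited form, so it does not by itself contradict the collection window. The gap is that 6.8.2 states none.
- **A handful of AE stoppers makes discontinuation significant by definition.** That holds for the stopping reason as a factor, not for the yes/no item.

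SAP 4.3 may define the long-term classifier and 6.8.3 may list the tested factors. Those two sub-points are therefore conditional. The 6.8.2 split itself does not depend on them.

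**Conclusion.** The point holds in a limited form and should be fixed. The 6.8.2 split conditions on achieved duration, which AEs can shorten. Its long-term column describes patients who remained on drug, and the short-versus-long contrast cannot be read as a duration effect because it can take either sign without one.

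The size rests entirely on assumed rates. Counted to Visit 3 under the stated assumptions, the gap to the full set is 1.1 points at 10% AE-driven stopping (within sampling error), 3.7 at 25% and 6.4 at 40%. The direction against the full set depends on how many patients stop for other reasons and when.

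A reader might infer that the study's main safety result is biased by this. The documents do not support that, because the full-set tables do not use the split.

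On the tests, protocol 8.7.1 and 8.7.2 read together make an AE stopping reason a factor for AE occurrence, which is circular. They also make long-term use and total period of drug use factors although AEs affect both. SAP 6.8.3 may narrow this. Confidence is medium.

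**What to change.** 1. Keep the split table as descriptive. Footnote it as conditional on achieved duration and not an estimate of 24-week risk, and state its AE counting window.
2. In the full safety set, add AE incidence by time since first dose (0–<12, 12–24 and >24 weeks) with patients at risk. Add cumulative incidence at weeks 12 and 24, censored at the earlier of last contact and 30 days after last dose. Under the assumptions above these would be 1 − 0.8^0.5 = 10.6% and 20.0% whatever the level of AE-driven stopping. State that this relies on other-reason stopping being unrelated to AE risk; the simulation builds that in and does not prove it.
3. Do not test early-termination reason, total period of drug use or long-term use as factors for AE occurrence, and do not count them toward the SAP 5.5 logistic-regression trigger. Report them descriptively.
4. Unless SAP 4.3 already does so, use one classifier for long-term use, namely the SAP 7.1 administration period, with a stated day tolerance around Visit 3. Without one, a completer who starts at Visit 1 and is seen two days early has 166 + 1 = 167 days and is filed as short-term. A tolerance repairs the label, not the depletion.

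The cost is SAP wording, a few extra tables and a rule for AEs with partial onset dates. Onset and dosing dates are already collected.
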